- l. SpO₂ will be assessed Q4h (± 30 minutes) while the subject is hospitalized through Day 7. In case the last SpO₂ assessment on Day 7 was performed after 8 PM, the first SpO₂ assessment on Day 8 should be performed within 8 hours from the last SpO₂ assessment on Day 7. For subjects who remain hospitalized after Day 7, SpO₂ assessment should then continue Q8h (± 1 hour) until 24 hours after the cessation of supplemental oxygen.
- m. A complete physical examination includes all body systems.
- n. A directed physical examination includes respiratory system, nose, ear, throat, facial and neck lymph nodes, and skin examination.
- o. A 12-lead ECG is strongly preferred but in cases where a 12-lead ECG is not possible or feasible, then a 6-lead ECG may be performed.
- p. An ECG needs to be recorded on Day 4 for subjects who remain hospitalized at this time. If discharged earlier than Day 4, the subjects need to have an ECG recorded on the day of discharge. The ECG will be performed 30 minutes to 3 hours after the first dose of that day.
- q. Leftover blood samples and nasal swabs may be used for exploratory biomarker analyses.
- r. The mid-turbinate nasal swab or endotracheal sample taken during screening is placed in 3 mL of transport media and split into several aliquots. Assessments for RSV diagnosis at screening will be performed by a local laboratory and confirmed by a central laboratory. Other assessments will be done by a central laboratory.
- s. Mid-turbinate nasal swabs (from the same nostril throughout the study) and/or endotracheal samples to assess RSV viral load and resistance should be taken by a trained study team member from Day 1 to Day 6 and on Day 7, Day 10, Day 14, and Day 28. Samples should be taken at approximately the same time each day prior to study drug administration. In case of nostril bleeding or irritation during the collection of a mid-turbinate nasal swab, all subsequent nasal swabs will be

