8. PRESTUDY AND CONCOMITANT THERAPY

Prestudy therapies administered up to 7 days before first dose of study drug must be recorded at screening.

All subjects will receive supportive care according to local institution standards and applicable guidelines. While treatment guidelines and standards vary based on local practice and should be considered in the management of subjects, within the parameters of this study, it is recommended that supplemental oxygen can be administered or withdrawn, as appropriate, to maintain an SpO₂ \geq 93% as long as it is medically indicated (for subjects whose baseline SpO₂ is \geq 93% when clinically stable).

Concomitant therapies must be recorded throughout the study beginning with start of the first dose of study drug to the Day 28 visit (\pm 2 days). During hospitalization, concomitant medication will be recorded by the site staff in the eCRF. Upon discharge, parent(s)/caregiver(s) will be required to document use of concomitant medication in the electronic device in a medication log, which will serve as basis for recording in the eCRF by the site staff. Concomitant therapies should also be recorded beyond Day 28 in the subject's medical notes and reported by SAE forms (if applicable).

All therapies (prescription or over-the-counter medications, including vaccines, vitamins, herbal supplements, home oxygen therapy and non-pharmacologic therapies such as electrical stimulation, acupuncture, special diets, exercise regimens) different from the study drug must be recorded in the eCRF. Recorded information will include a description of the type of the drug/therapy, treatment phase, dose regimen, route of administration, and its indication.

Modification of an effective preexisting chronic therapy should not be made for the explicit purpose of entering a subject into the study; however, if a subject has received acute doses of a prohibited drug, switching to an alternative drug chosen at the discretion of the investigator should be allowed.

Concomitant medications are permitted as indicated for the management of study subjects with the exception of the medications noted here. The following medications are not permitted during the study and for the time period prior to randomization as noted:

- Moderate/strong inhibitors of OAT3: diclofenac, diflunisal, gemfibrozil, mycophenolic acid, piperacillin, probenecid, and teriflunomide (all within 24 hours prior to randomization).

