Attachment 2: Cardiovascular Safety – Abnormalities

Electrocardiogram

All important abnormalities from the ECG readings will be listed.

Parameter (unit)	Age class	Abnormally low	Abnormally high
PR (msec)	0 - 2 years	NA	>150
	2 - <3 years	<100	>150
QRS (msec)	0 - 2 years	NA	>79
	2 - <3 years	<40	>79
QT (msec)	0 - 2 years	NA	>500
	2 - <18 years	<320	>450
RR (msec)	0 - 3 months	<333	>750
	3 - 12 months	<400	>860
	1 - 2 years	<430	>1000
	2 - <18 years	<600	>1200

Vital Signs

Normal ranges:

Parameter (unit)	Age class				
	0 - 3 months	3 - 6 months	6 - 12 months	1 - 2 years	2- <3 years
Diastolic BP (mmHg)	45 - 55	50 - 65	55 - 65	55 - 70	45 - 60
Systolic BP (mmHg)	65 -85	70 - 80	80 - 100	90 - 105	85 - 100
Heart rate HR (bpm)	100 - 150	90 - 120	80 - 120	70 - 110	95 - 125
Respiratory rate	35 - 55	30 - 45	25 - 40	20 - 30	22 - 30
Oxygen saturation SpO ₂ (%)	≥96	≥96	≥96	≥96	≥96

The following clinically relevant abnormalities will be defined for vital signs

Parameter (unit)		Age class			
		0 - 3 months	3 - 12 months	1 - 2-years	2- <3 years
Diastolic BP (mmHg)	abnormally low	<35	<40	<40	<40
	abnormally high	>65	>85	>90	>70
Systolic BP (mmHg)	abnormally low	<60	<60	<75	<80
	abnormally high	>110	>110	>120	>110
Heart rate HR (bpm)	abnormally low	<80	<70	<60	<90
	abnormally high	>180	>150	>140	>130
Respiratory rate	abnormally low	<25	<20	<18	<20
	abnormally high	>70	>60	>50	>35
Oxygen saturation SpO ₂ (%)	abnormally low	<92	<92	<92	<92

References: Normal ranges for vital signs based on the following references and internal pediatrician insight:

Kliegman RM, Stanton B, St Geme J, Schor N, Behrman RE. *Nelson Textbook of Pediatrics*, 19th Edition.

Attachment 3: Guideline for the Estimation of Glomerular Filtration Rate (GFR) Based on Serum Creatinine in Children

- The production of creatinine is proportional to muscle mass, which is in turn related to body mass and height (for normally proportioned individuals). Therefore in a steady-state situation the GFR can be estimated from the plasma creatinine according to Schwartz formula (for serum creatinine measured by Jaffe methodology):

$$\text{Children 1-12 years}^1: \quad e\text{GFR} = \frac{0.55 \times \text{length (cm)}}{\text{Serum creatinine (mg/dL)}}$$

- The Schwartz formula is modified for different age groups and sexes:

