6.3.1. Definitions

The vital signs abnormalities will be defined as indicated in [Attachment 2](#). In determining the abnormalities, the following rules are applied:

- worst grades/abnormalities are determined over the whole observational period for each trial phase separately, including post-baseline scheduled and unscheduled measurements of that phase.
- The abnormalities ‘abnormally low’ and ‘abnormally high’ /grades are considered equally important, i.e. if a subject has as well an abnormally low as an abnormally high or graded value post-baseline, both abnormalities are shown in the tables. (This means that the sum of the percentages can be more than 100%)

An abnormality will be considered emergent in a particular phase if it is worse than baseline. If baseline is missing, the abnormality is always considered as emergent. A shift from ‘abnormally low’ at baseline to ‘abnormally high’ post baseline (or vice versa) is also emergent.

Note: As described in section 2.1, for vital signs, means per analysis timepoint window will be calculated in order to have 1 assessment per analysis timepoint. These mean values per analysis timepoint will be used in the descriptive analyses over time. Abnormalities, to be used in the determination of the worst abnormality per phase, will not be determined on these mean values, but on the original records, including both scheduled and unscheduled assessments.

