6.3.2. Analysis Methods

Actual values and change from baseline will be summarized by treatment group at each scheduled time point.

A cross-tabulation of the worst toxicity/abnormality versus baseline will be presented per phase (Treatment phase, Follow-up phase) and for the combination of Treatment and follow-up phase. This table will also show the number and percentage of subjects per worst toxicity/abnormality, the number and percentage of subjects per emergent worst toxicity/abnormality and the cumulative number of subjects per emergent toxicity/abnormality or worse.

Mean±SE graphs over time for the actual values and changes from baseline will be generated for all tests performed.

A listing of abnormal individual subject vital signs values will be provided. This listing will include all other time points for the corresponding subject/parameter.

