ATTACHMENT 2. : VITAL SIGNS

The following classes for vital signs abnormalities will be defined based on the references [1] and [2], and internal pediatrician insight at J&J:

Parameter (unit)	Abnormality class	Age class				
		0 - 3 months	3 - 6 months	6 - 12 months	1 - 2-years	2- <3 years
Diastolic BP (mmHg)	abnormally low clinically relevant	<35	<40	<40	<40	<40
	abnormally low not clinically relevant	35 - <45	40 - <50	40 - <55	40 - <55	40 - <45
	Normal	45 - 55	50 - 65	55 - 65	55 - 70	45 - 60
	abnormally high not clinically relevant	>55 - 65	>65 - 85	>65 - 85	>70 - 90	>60 - 70
	abnormally high clinically relevant	>65	>85	>85	>90	>70
Systolic BP (mmHg)	abnormally low clinically relevant	<60	<60	<60	<75	<80
	abnormally low not clinically relevant	60 - <65	60 - <70	60 - <80	75 - <90	80 - <85
	Normal	65 - 85	70 - 80	80 - 100	90 - 105	85 - 100
	abnormally high not clinically relevant	>85 - 110	>80 - 110	>100 - 110	>105 - 120	>100 - 110
	abnormally high clinically relevant	>110	>110	>110	>120	>110
Heart rate HR (bpm)	abnormally low clinically relevant	<80	<70	<70	<60	<90
	abnormally low not clinically relevant	80 - <100	70 - <90	70 - <80	60 - <70	90 - <95
	Normal	100 - 150	90 - 120	80 - 120	70 - 110	95 - 125
	abnormally high not clinically relevant	>150 - 180	>120 - 150	>120 - 150	>110 - 140	>125 - 130
	abnormally high clinically relevant	>180	>150	>150	>140	>130
Respiratory rate	abnormally low clinically relevant	<25	<20	<20	<18	<20
	abnormally low not clinically relevant	25 - <35	20 - <30	20 - <25	18 - <20	20 - <22
	Normal	35 - 55	30 - 45	25 - 40	20 - 30	22 - 30
	abnormally high not clinically relevant	>55 - 70	>45 - 60	>40 - 60	>30 - 50	>30 - 35
	abnormally high clinically relevant	>70	>60	>60	>50	>35
Oxygen saturation SpO ₂ (%)	abnormally low clinically relevant	<92	<92	<92	<92	<92
	abnormally low not clinically relevant	92 - <96	92 - <96	92 - <96	92 - <96	92 - <96

Parameter	Abnormality class clinically relevant	Age class				
	Normal	≥96	≥96	≥96	≥96	≥96

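### The SAP classes SpO2 and flags emergent abnormalities without regard to supplemental oxygen, so weaning can register as an emergent low SpO2 and saturation held at 96% or above by support is tabulated as normal.

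*Protocol*

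**What the plan says.** Protocol section 2.1.2 lists SpO2 among the secondary safety and tolerability measures.

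- **Classes.** Protocol Attachment 2 gives a normal range of 96% or above and then states "The following clinically relevant abnormalities will be defined for vital signs", with one SpO2 limit, below 92%. SAP Attachment 2 states "The following classes for vital signs abnormalities will be defined" and uses three SpO2 classes: normal (96% or above), "abnormally low not clinically relevant" (92% to below 96%), and clinically relevant low (below 92%). The limits are the same at every age. Neither table has a room-air condition or an oxygen column.
- **Baseline.** SAP 2.6 takes the last record before first intake, whatever support the child was on.
- **Emergent rule.** SAP 6.3.1: "An abnormality will be considered emergent in a particular phase if it is worse than baseline". The worst class per phase is judged not on window means "but on the original records, including both scheduled and unscheduled assessments".
- **Outputs.** SAP 6.3.2 cross-tabulates the worst abnormality per phase against baseline, counts emergent abnormalities, and adds: "Actual values and change from baseline will be summarized by treatment group at each scheduled time point". SAP 2.1 averages SpO2 readings within 8-hour windows.
- **Oxygen practice.** In protocol section 8, "it is recommended that supplemental oxygen can be administered or withdrawn, as appropriate", to maintain SpO2 at 93% or above.
- **Timing.** Footnote l of the hospitalization Time and Events Schedule sets readings every 4 hours through Day 7 regardless of oxygen. For children still in hospital after Day 7, readings are every 8 hours "until 24 hours after the cessation of supplemental oxygen".

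**The concern.** A saturation reading cannot be interpreted without knowing the support behind it. In this trial oxygen is adjusted to the reading, and the protocol's design rationale (section 3.2) expects treatment may reduce the need for it. Exclusion criterion 8 removes children on chronic home oxygen, so most children on oxygen at baseline should later contribute room-air readings.

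A table that compares a room-air reading with an on-oxygen baseline, on value alone, can record a step in recovery as a new abnormality. The same table cannot distinguish a normal saturation on room air from one held up by ventilation. If the arms differ in how fast children come off oxygen, their SpO2 safety tables may differ for that reason alone.

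**Working it through.** The plan states no figure on this point, so the check is to apply its own rules.

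**Step 1: rules.** From SAP Attachment 2, class 0 is SpO2 ≥96, class 1 is 92 to <96, and class 2 is <92. From SAP 6.3.1, a record is emergent if its class is higher than the baseline class. Oxygen status does not enter either rule.

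**Step 2: weaning.** The SpO2 values are illustrative assumptions, and the second reading is taken as the worst in the phase.

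| Baseline | Worst later reading | Class change | Emergent? |
|---|---|---|---|
| 97% on oxygen | 94% room air | 0 to 1 | yes, not clinically relevant class |
| 97% on oxygen | 93% room air | 0 to 1 | yes, not clinically relevant class |
| 97% on oxygen | 96% room air | 0 to 0 | no |
| 94% on oxygen | 94% room air | 1 to 1 | no |
| 97% on oxygen | 91% room air | 0 to 2 | yes, clinically relevant |

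The first two rows meet the 93% level in protocol section 8 and are still emergent. They cross no limit in protocol Attachment 2, where only values below 92% count. They therefore do not meet the Attachment 2 definition of a clinically relevant abnormality, which protocol section 9.7 sends to the AE page.

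**Step 3: support.** A child at 94% on room air at baseline whose readings in the phase are all 96% or above on ventilation goes from class 1 to class 0: normal, not emergent. One earlier low reading in that phase would remain as the worst record, because the table keeps the worst class on original records. A child at 97% on room air who reads 94% on ventilation goes from class 0 to class 1 and is emergent.

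**Step 4: means.** With readings every 4 hours and windows of 8 hours, a window holds 8/4 = 2 scheduled readings, which can straddle the stop of oxygen. At arm level, let p be the share of readings on oxygen and d the on-oxygen mean minus the room-air mean. The arm mean is the room-air mean plus p × d, so two arms alike in all else differ by (p₁ − p₂) × d. If p is assumed to be 0.60 and 0.40, the difference is 0.20 × d: 0.2, 0.4 or 0.6 points for an assumed d of 1, 2 or 3. It is zero if d is zero and changes sign if d is negative. The documents give neither p nor d.

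**Step 5: do other outputs correct this?** Protocol 11.8 promises an overview of subjects requiring oxygen, but SAP 6.3.2 does not repeat it. SAP 5.3.1.3 defines oxygen and ventilation requirement (only in children not already on the relevant support before first dose), time to end of each support, and time to SpO2 of at least 93% on room air. None of these changes the class of an SpO2 record.

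**The case against.** The strongest reply is that the oxygen information is in the trial and that the affected table is descriptive. Protocol 11.8 plans no statistical testing of safety. Baseline oxygen use, oxygen requirement, time off support and the room-air endpoint are all reported by arm, so faster weaning would show there directly. The abnormality listing carries each subject's other readings. The weaning example reaches only a class that the SAP itself labels as not clinically relevant. All of this stands, and it keeps the point modest. It does not repair the SpO2 table, which a safety reader would take at face value.

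Several stronger readings are tempting but unsupported:

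- A reader might infer that every weaned child becomes emergent. The class must fall below the baseline class.
- A reader might infer that any ventilated child is shown as normal. That needs every reading in the phase to be 96% or above.
- A reader might attribute the 92% to below 96% abnormal class to the protocol. It is defined only in the SAP.
- A reader might take the 24-hour rule in footnote l as governing all readings. It applies only after Day 7 in hospital.
- A reader might conclude that benefit will read as harm. Oxygen is adjusted to the reading, and children off oxygen may be the recovered ones, so the gap between on-oxygen and room-air readings could be nil or reversed.

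There is also a fair objection to the obvious remedy. Classing only room-air readings would leave 88% on a ventilator unclassed. Barring an on-oxygen-to-room-air shift from being emergent would hide a fall from 97% on oxygen to 88% on room air. Neither should be adopted.

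**Conclusion.** The point holds as a defect in how the SpO2 safety data are presented. SAP Attachment 2 and SAP 6.3.1 class readings and flag emergence without oxygen status. A fall in class on weaning can therefore count as an emergent abnormality, and saturation held at 96% or above throughout a phase by support is shown as normal. The means mix both kinds of reading.

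The size and direction of any arm difference cannot be computed: the documents give no SpO2 distribution, no share of children on oxygen at baseline and no weaning rates. A count of subjects flagged by worst class would need all three. The conclusion rests only on the text of the classes, the baseline definition and the emergent rule. The primary endpoint and the limit of below 92% are not in question.

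**What to change.** Amend SAP 6.3.1 and 6.3.2 before unblinding:

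1. Link each SpO2 record, including baseline, to the Oxygen Supplementation form. The room-air SpO2 endpoint in SAP 5.3.1.3 already needs this link.
2. Keep every reading classed and every flag below 92%, whatever the support.
3. Show the worst-versus-baseline cross-tabulation and the emergent counts by oxygen status at baseline and at the worst record: room air, non-mechanical oxygen, non-invasive ventilation, invasive ventilation.
4. Identify shifts from an on-oxygen baseline to a room-air reading as a separate line within the emergent count, not removed from it.
5. Summarise SpO2 means and changes by oxygen status alongside the overall summary.

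The cost is SAP wording and one merge of data already collected. Cells will be smaller. Oxygen status after first dose is a post-randomization variable, so the by-status summaries compare selected children and should be labelled descriptive only.

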Attachment 4: Visit Schedule for Rash Management in Pediatric Subjects

This visit schedule summarizes the visits and assessments to be performed in case of rash. At the investigator's discretion, additional visits and assessments can be performed.

	Grade 1 Rash	Grade 2 Rash	Grade 3 or 4 Rash
Day 1 of rash ¹	
 Study medication may be continued. Unscheduled visit for initial rash evaluation REQUIRED. Digital pictures REQUIRED (preferably within 24h). Referral to dermatologist (preferably within 24h) ONLY IF rash diagnosis or relationship with study medication is uncertain. 	
 Study medication MUST be permanently DISCONTINUED. Rechallenge is NOT ALLOWED. Unscheduled visit for initial rash evaluation REQUIRED. Digital pictures REQUIRED (preferably within 24h). Referral to dermatologist (preferably within 24h) ONLY IF rash diagnosis or relationship with study medication is uncertain. 	
 Study medication MUST be permanently DISCONTINUED. Rechallenge is NOT ALLOWED. Unscheduled visit for initial rash evaluation REQUIRED. Digital pictures REQUIRED (within 24h). Referral to dermatologist REQUIRED (preferably within 24h). At discretion of the investigator or at request of the dermatologist, assessment of safety blood sample. Biopsy ONLY IF required by dermatologist.
Day 2	
 Follow-up visit REQUIRED.² Digital pictures REQUIRED. 	
 Follow-up visit REQUIRED.² Digital pictures REQUIRED. 	
 Follow-up visit REQUIRED. Digital pictures REQUIRED.
Day 3	No rash follow-up visit required. ²	No rash follow-up visit required. ²	
 Follow-up visit REQUIRED. Digital pictures REQUIRED. At discretion of the investigator or at request of the dermatologist, assessment of safety blood sample.

¹ Note that Day 1 of the rash is the first day of investigator assessment and not the first day of rash as reported by the subject and that the following days are in relation to this first assessment (not study days)

² In case rash progresses from a grade 1 or a grade 2 to a higher grade, start follow-up schedule for grade 2, 3, or 4 rash as appropriate.

	Grade 1 Rash	Grade 2 Rash	Grade 3 or 4 Rash
Day 4	No rash follow-up visit required. ²	No rash follow-up visit required. ²	
 Follow-up visit REQUIRED. Digital pictures REQUIRED. At discretion of the investigator or at request of the dermatologist, assessment of safety blood sample.
Day 5	No rash follow-up visit required.	No rash follow-up visit required. ²	
 Follow-up visit REQUIRED. Digital pictures REQUIRED. At discretion of the investigator or at request of the dermatologist, assessment of safety blood sample.
Day 6	No rash follow-up visit required. ²	No rash follow-up visit required. ²	
 Follow-up visit REQUIRED. Digital pictures REQUIRED. At discretion of the investigator or at request of the dermatologist, assessment of safety blood sample.
Day 7	No rash follow-up visit required. ²	No rash follow-up visit required. ²	No Rash follow-up visit required.
Day 8	
 Follow-up visit REQUIRED.² Digital pictures REQUIRED. 	
 Follow-up visit REQUIRED.² Digital pictures REQUIRED. 	No Rash follow-up visit required.
Further Visits	If rash is unresolved after second follow-up visit, further visits (with digital pictures) at the investigator's discretion. ²	If rash is unresolved after second follow-up visit, further visits (with digital pictures) at the investigator's discretion. ²	Weekly follow-up visits REQUIRED (with digital pictures) until resolution of grade 3-4 rash to grade ≤ 2 rash (further follow-up visits according to grade 1 or grade 2 rash instructions).

² In case rash progresses from a grade 1 or a grade 2 to a higher grade, start follow-up schedule for grade 2, 3, or 4 rash as appropriate.

Attachment 5: Pediatric RSV Electronic Severity and Outcome Rating System (PRESORS)v6 – Clinician’s Electronic Clinical Outcome Assessment and Caregiver Diary

Clinician’s electronic clinical outcome assessment (eCOA)

[Assessment initiation step – Use eCOA Clinician log in screen but ensure the following are recorded _____ indicates instructions for programming eCOA _____ indicates entry in the device]

Site ID _____

Clinician ID _____

Clinician PW _____

Enter/confirm patient ID _____

Confirm date _____

Confirm time _____

First question (asked at screening only):

1. Why was this subject hospitalized?
 - 1.1 Was the subject hospitalized due to any of these clinical signs? (note all that apply)
 - Apnoea
 - Respiratory distress (eg, cyanosis, tachypnea, retractions)
 - Low oxygen saturation
 - Tachycardia
 - None of these
 - 1.2 Was the subject hospitalized due to any of these clinical signs? (note all that apply)
 - Dehydration/difficulty feeding
 - Listless or unresponsive
 - Fever
 - Need for clinical monitoring
 - None of these
 - 1.3 Was the subject hospitalized for any other reason?
 - No
 - Yes → *(specify pop-up: please specify [256 character free-text])*

[Intro screen for current/recent status assessment]

Please record the following information regarding the subject's status during the past 12 hours.

1. Describe the subject's reported worst activity level during the past 12 hours (select one)
 - Alert and active/normal sleep
 - Irritable/restless/agitated
 - Floppy/lethargic/poor interaction
 - Only responds to pain/unresponsive

2. Describe how the subject slept during the past 12 hours (select one)
 - Normal
 - Occasional restlessness/disturbed
 - Restless/disturbed much of the time
 - Comatose

3. Signs of increased work of breathing during the past 12 hours
 - 3.1. Did the subject show any of these signs (or reports) of increased work of breathing during the past 12 hours? (note all that apply)
 - Subcostal retractions
 - Intercostal retractions
 - Tracheosternal retractions
 - Tachypnea [*tachypnea needs defined within the system WHO values pop-up?*]
 - None of the above [*cannot be checked if any other options selected*]

 - 3.2. Did the subject show any of these signs (or reports) of increased work of breathing during the past 12 hours? (note all that apply)
 - Nasal flaring
 - Head bobbing
 - Grunting
 - Other signs of increased work of breathing not already reported
 - None of the above [*cannot be checked if any other options selected*]

4. During the past 12 hours, are there observations/reports of the subject experiencing any of the following? (note all that apply)
 - Cyanosis
 - Apnoea
 - Cough
 - Nasal secretions
 - Wheezing
 - None of the above reported [*cannot be checked if any other options selected*]

5. How did the subject feed in the past 12 hours? (select one)

- >75% of normal amount of feeds via usual route
- 50% to 75% of normal amounts of feeds via usual route
- <50 % of normal feeds or needing NG feeds or IV fluids

Please record the following information regarding the subject's status now.

6. Describe the subject's activity level now (select one)

- Alert and active/normal sleep
- Irritable/restless/agitated
- Floppy/lethargic/poor interaction
- Only responds to pain/unresponsive

7. Signs of increased work of breathing now

7.1. Does the subject show any of these signs of increased work of breathing now? (note all that apply)

- Subcostal retractions
- Intercostal retractions
- Tracheosternal retractions
- Tachypnea [*tachypnea needs defined within the system WHO values pop-up?*]
- None of the above [*cannot be checked if any other options selected*]

7.2. Does the subject show any of these signs of increased work of breathing now? (note all that apply)

- Nasal flaring
- Head bobbing
- Grunting
- Other signs of increased work of breathing not already reported
- None of the above [*cannot be checked if any other options selected*]

8. Does the subject show any signs of cyanosis?

- Yes
- No

9. Describe the subject's coughing now (select one)

- Little or no coughing
- Occasional strong cough, sometimes productive
- Frequent cough, sometimes causing choking, gagging, or vomiting

10. Describe the subject's nasal secretions now (select one)

- None
- Minimal, easily cleared with suctioning
- Moderate, but could be cleared with suctioning
- Extensive, requires frequent suctioning

11. Describe the subject's wheezing now (select one)

- No wheezing
- Terminal expiratory wheezing or only with stethoscope
- Entire expiration or audible during expiration without stethoscope
- Inspiration and expiration without stethoscope

12. Does the subject appear to be dehydrated now?

- Yes
- No

13. Do you have any concerns relating to the subject's overall condition? (select one)

- No concerns (condition is stable or improving)
- Some concerns (may become unstable/requires close observation)
- Extremely concerned (unstable, requires immediate medical review)

14. Overall, how would you rate the subject's current health status? (select one)

- Excellent
- Good
- Fair
- Poor

During hospitalization only:

15. Based on the clinical status of the subject, is the subject ready to be discharged?

- Yes
- No

At the Day 7 visit only (only for studies in which study drug is administered):

16. In general, was the oral dosing of the study medication well tolerated by the subject?

- Yes
- No

17. Study drug administration

17.1 During study drug administration, were any of the following reported? (note all that apply)

- Disgusted expressions after tasting medicine
- Cried after tasting medicine
- Refused (would not open mouth or turned head away to avoid medicine)
- None of these were reported [*cannot be checked if other options selected*]

17.2 During study drug administration, were any of the following reported? (note all that apply)

- Spit out or coughed out medicine
- Gagged or wretched
- Vomited (within 2 minutes of swallowing medicine)
- None of these were reported [*cannot be checked if other options selected*]

At Day 7 and during the end-of-study visits only, clinicians will be asked the following clinician's global rating of change (CGRC) question:

18. With respect to the child's RSV infection, how would you describe the child's health now compared to the baseline assessment?

-5	-4	-3	-2	-1	0	1	2	3	4	5
Very much worse					Unchanged					Very much better

Screen shown after final question for the assessment has been entered.

Thank you for completing this assessment.

Pediatric RSV Electronic Severity & Outcome Rating System (PRESORS) v6**Caregiver diary**

[completed at screening and throughout the study until the end of follow-up]

Enter your user ID

Enter your passcode

Caregiver demographic questions 1-7 to be completed the first time the caregiver completes the diary

1. How are you related to the child in this study? (select one)

- Parent, step parent, or foster parent
- Grandparent
- Other family member
- Nanny or day care provider
- Neighbor or friend of the parent
- Other

2. Do you live with the child in this study? Yes No

3. There are 168 hours in a week. Counting time even when the child is asleep, how many hours do you usually take care of the child each week? hours/week

4. What year were you born? year born

5. Are you male or female? Male Female

6. How many years of education have you completed? years

7. What best describes your employment status? (select one)

- Full-time paid employment
- Full-time homemaker
- Part-time paid employment
- Retired
- Disabled, unable to work due to health problems
- Unemployed, looking for work
- Other

Caregiver diary entry to be completed by caregiver at each assessment except as noted

PRESORS Caregiver diary

It is now time to complete your caregiver diary.

For each question, please mark the answer or answers that best describe how the child has been *[during the appropriate recall period for the assessment, see table below]*

Assessment timing	Recall language
Screening and baseline (If ≥ 12 hours post screening)	“over the last 12 hours”
Twice daily post baseline through Day 14	
Upon waking in the morning	“since bedtime last night”
Evening at the child’s usual bedtime	“since the child woke up this morning”
For studies with more than 7 days follow-up post baseline, once daily in the evening assessments from Day 15 through end of follow-up	“since this time yesterday”
At the Day 28 post-treatment follow-up visit	“over the last 24 hours”

1. Overall, how has the child’s health been *[recall period]*?

- Excellent
- Good
- Fair
- Poor

2. If the child was awake at all *[recall period]*, how active was the child?

- As active as usual
- A little less active than usual
- A lot less active than usual
- Floppy or limp, not responding to you as usual

For 12-hour recall phase use Question 3a

3a. How much did the child sleep *[recall period]*? (select one)

- A lot less than usual
- A little less than usual
- About as much as usual
- A little more than usual
- A lot more than usual

For 24-hour recall phase use Questions 3b and 3c

- 3b. How much did the child sleep during the day during the past 24 hours? (select one)
- A lot less than usual
 - A little less than usual
 - About as much as usual
 - A little more than usual
 - A lot more than usual
- 3c. How much did the child sleep during the night during the past 24 hours? (select one)
- A lot less than usual
 - A little less than usual
 - About as much as usual
 - A little more than usual
 - A lot more than usual
4. Was the child crying more than usual [*recall period*]? (select one)
- Normal, no more crying than usual
 - Cried more than usual but calmed if held or soothed
 - Cried a lot, difficult to calm even if held or soothed
 - Cried a lot, would not stop crying even if held or soothed
5. Do you hear wheezing or whistling sounds in the child's chest when the child breathes? (select one)
- No
 - Yes, but only at the end of when the child breathes out
 - Yes, throughout breathing out
 - Yes, throughout breathing in and out

6. There are signs you can see when a child has breathing problems.
- 6.1. Did the child show these signs of breathing problems [*recall period*]? (note all that apply)
- Breathing through mouth because of difficulties breathing through stuffy or runny nose
 - Gasping for air and/or long pauses between breaths
 - Breathing faster than usual
 - None of these [*option cannot be checked if any of the other options are selected*]
- 6.2. Did the child show any of these signs of breathing problems [*recall period*]? (note all that apply)
- Ribs more visible than usual when child breathes in
 - Skin at the base of the throat sucked in when breathing in
 - Belly sucked in when breathing in
 - None of these [*option cannot be checked if any of the other options are selected*]
- 6.3. Did the child show any of these signs of breathing problems [*recall period*]? (note all that apply)
- Nostrils flared out when breathing in
 - Head bobbed back and forth when breathing
 - Made grunting sounds when breathing
 - None of these [*option cannot be checked if any of the other options are selected*]
7. Did the child's lips, skin or fingernails look pale or blue [*recall period*]? (select one)
- No
 - Yes, but only when the child was crying
 - Yes, even when the child had not been crying
8. Did the child cough [*recall period*]? (select one)
- No coughing
 - A little coughing
 - Coughing a lot
 - Coughing almost all the time
9. Did the child spit up more often than usual [*recall period*]? (select one)
- spit up about as often as usual
 - spit up a little more often than usual
 - spit up a lot more often than usual
10. Did the child vomit [*recall period*]? (select one)
- No [*→ Question 10*]
 - Yes [*→ Question 9.1*]

